5.2.6.2 Adverse event collection and reporting

5.2.6.2.1 AE Collection

The investigator shall maintain and keep detailed records of all AEs in the patient files. The following must be collected and documented on the appropriate CRF(s) by the investigator:

- From signing the informed consent onwards until the individual patient's end of trial (the End of Trial (EoTrial) visit):
all AEs (serious and non-serious) and all AESIs.
- After the individual patient's end of trial:
the investigator does not need to actively monitor the patient for new AEs but should only report any occurrence of cancer and trial treatment related SAEs and trial treatment related AESIs of which the investigator may become aware of by any means of communication, e.g. phone call. Those AEs should be reported on the BI SAE form (see [Section 5.2.6.2.2](#)), but not on the CRF.

Vital Status Data Collection

Patients who discontinue trial medication prematurely, who agree to be contacted further but do not agree to physical visits, should be followed up as described in [Section 3.3.5.1](#), withdrawal from trial treatment. From then on until the individual patient's end of the trial the investigator must report all deaths/fatal AEs regardless of relationship, and trial treatment related SAEs and trial treatment related AESIs the investigator becomes aware of.

5.2.6.2.2 AE reporting to the sponsor and timelines

The investigator must report SAEs, AESIs, and non-serious AEs which are relevant for the reported SAE or AESI, on the BI SAE form immediately (within 24 hours) to the sponsor's unique entry point (country specific contact details will be provided in the ISF). The same timeline applies if follow-up information becomes available. In specific occasions, the investigator could inform the sponsor upfront via telephone. This does not replace the requirement to complete and send the BI SAE form.

With receipt of any further information to these events, a follow-up SAE form has to be provided. For follow-up information the same rules and timeline apply as for initial information. All (S)AEs, including those persisting after individual patient's end of trial must be followed up until they have resolved, have been assessed as "chronic" or "stable", or no further information can be obtained.

5.2.6.2.3 Pregnancy

In rare cases, pregnancy might occur in a clinical trial. Once a patient has been enrolled in the clinical trial and has taken trial medication, the investigator must report any drug exposure during pregnancy in a trial participant immediately (within 24 hours) by means of Part A of the Pregnancy Monitoring Form to the sponsor's unique entry point.

Similarly, potential drug exposure during pregnancy must be reported if a partner of a male trial participant becomes pregnant. This requires written consent of the pregnant partner. Reporting and consenting must be in line with local regulations. The ISF will contain the trial specific information and consent for the pregnant partner.

The outcome of the pregnancy associated with the drug exposure during pregnancy must be followed up and reported to the sponsor's unique entry point on the Pregnancy Monitoring Form for Clinical Studies (Part B).

The ISF will contain the Pregnancy Monitoring Form for Clinical Studies (Part A and B).

As pregnancy itself is not to be reported as an AE, in the absence of an accompanying SAE and/or AESI, only the Pregnancy Monitoring Form for Clinical Studies and not the SAE form is to be completed. If there is an SAE and/or AESI associated with the pregnancy an SAE form must be completed in addition.

5.3 DRUG CONCENTRATION MEASUREMENTS AND PHARMACOKINETICS

Not applicable.

5.4 ASSESSMENT OF BIOMARKER(S)

Not applicable.

5.5 BIOBANKING

Not applicable.

5.6 OTHER ASSESSMENTS

Not applicable.

5.7 APPROPRIATENESS OF MEASUREMENTS

Not applicable.

6. INVESTIGATIONAL PLAN

In the event of force majeure or other disruptive circumstances (e.g. pandemic, war) the investigational plan as per this clinical trial protocol may not be feasible at a site. With the consent of the patient, sponsor and investigator may agree on alternative, back-up or rescue methodology which may include but will not be limited to virtual patient visits and assessments, home healthcare nurse visits, and direct-to-patient shipments of trial treatment. Such alternative measures may be described in a specific Crisis Management Manual as part of the initial submission package, and will also be mentioned in the patient information leaflet. The implementation of these measures will depend on patient's consent, operational feasibility, local law and regulations. If alternative methodology is implemented, the deviations from the original plan will be precisely documented.

6.1 VISIT SCHEDULE

The study will consist of three sequential periods, a Screening period of up to 8 weeks, a treatment period of 52 weeks and a follow-up period of 1 week. The maximum duration is expected to be 437 days.

After giving his/her informed consent, the patient will be screened for inclusion (see [Section 3.3.2](#)) and exclusion criteria (see [Section 3.3.3](#)) for the trial at Visit 1 and Visit 2 (refer to [Flow Chart](#)).

Visit 2 can be performed once the results from central laboratory of Visit 1 and central HRCT review are obtained. If for any reason the screening phase for an individual patient lasts for more than 6 weeks, then the laboratory examination for Visit 1 has to be repeated before randomization. The screening phase must be no longer than 8 weeks. The patient will be randomized at Visit 2 if all inclusion and none of the exclusion criteria are fulfilled.

The results of laboratory parameters from Visit 2 will become available only after Visit 2. Therefore, laboratory results from Visit 2 cannot qualify as exclusion criteria; laboratory results from Visit 1 will be used instead. In case laboratory results of Visit 2 would retrospectively fulfil an exclusion criterion, the patient should not continue receiving trial medication unless continuation is justified in writing by the Investigator.

A window of ± 3 days for Visits 3 to 6, ± 7 days for Visits 6a to 9 is allowed to accommodate scheduling problems. If a delay is observed for a particular visit, the original calendar schedule should be kept for subsequent visits (delays should not accumulate).

If treatment is discontinued, an end of treatment visit (EOT) will be performed in all patients.

If a patient misses an appointment, it will be rescheduled if possible. The relevance of measurements outside the permitted time windows will be assessed no later than at the Report Planning Meeting.

In exceptional cases, if standard visits at the trial sites are impossible because of COVID-19 related safety risks, the investigator needs to further discuss with the sponsor and then makes a decision how to arrange the related visits.

All home/remote visits need to be discussed with and approved by the sponsor's trial team. Local regulatory and legal requirements still apply.

For the details of the modifications refer to [Section 6.2](#).

All COVID-19 related deviations from the original schedule of visits and procedures will be documented and the implications considered for the analysis of the trial data.

Except for visit 1, visit 2 and EOT visit, in the event of force majeure or other disrupting circumstances the other visits may have to be performed at the patient's home after alignment with sponsor, remotely (by phone) or as a combination of home and remote visits. At these visits, the following assessments can be performed at the Patient's home or remotely:

- Concomitant therapy
- Pregnancy testing (urine) if need
- review results if some assessments can be done at local hospital except for FVC, please refer to [Flow Chart](#) for more details.
- all AEs / SAEs / AESIs
- IRT call after completing the above assessment, include the test results review from local laboratory
- Dispense trial medication
- compliance check

Trial medication will not be collected at visits performed remotely. Instead, the medication should be collected when the patient next visits the site, or when a visit is performed at the patient's home (see below).

The following assessments can be performed at the patient's home:

- vital signs
- physical examination if possible
- resting 12-lead ECG (using a portable ECG machine) if possible
- safety laboratory sampling and review of results if possible
- collect trial medication

If safety laboratory sampling via the central laboratory is not possible from the investigational site (and is instead performed at the patient's home or local hospital), analyses can be performed at a local laboratory. The results of the safety laboratory tests must be transferred to the Investigator who must ensure a medical review and document any clinically relevant safety issues as AEs. For a list of "minimum required safety laboratory parameters" refer to [Section 5.2.3](#) and [Table 5.2.3: 1](#).

When scheduling such visits every effort should be made to ensure a continuous supply of trial medication for the patient, whilst also taking into account that the next kit(s) of trial medication may need to be shipped from the site to the patient's home and, that medical prerequisites should be performed and confirmed prior to shipment of new supplies.

The investigators should ensure as much as possible that FVC assessment can be finished on site for every visit.

All deviations from the original schedule of assessments as defined in the Flow Chart will be documented and the implications considered for the analysis of the trial data.

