3.3.3 Exclusion criteria

1. AST and / or ALT $> 1.5 \times$ ULN at Visit 1
2. Bilirubin $> 1.5 \times$ ULN at Visit 1
3. Creatinine clearance $< 30 \text{ mL/min}$ calculated by Cockcroft–Gault formula at Visit 1.

[Note: Laboratory parameters from Visit 1 have to satisfy the laboratory threshold values as shown above. Visit 2 laboratory results will be available only after randomization. In case at Visit 2 the results do no longer satisfy the entry criteria, the Investigator has to decide whether it is justified that the patient remains on study drug. The justification for decision needs to be documented. Laboratory parameters that are found to be abnormal at Visit 1 are allowed to be re-tested (once) if it is thought to be a measurement error (i.e. there was no abnormal result of this test in the recent history of the patient and there is no related clinical sign) or the result of a temporary and reversible medical condition, once that condition is resolved].

4. Patients with underlying chronic liver disease (Child Pugh A, B or C hepatic impairment).
5. Previous treatment with nintedanib or pirfenidone.
6. Other investigational therapy received within 1 month or 6 half-lives (whichever was greater) prior to screening visit (Visit 1).
7. Use of any of the following medications for the treatment of ILD: azathioprine (AZA), cyclosporine, MMF, tacrolimus, oral corticosteroids (OCS) $> 20 \text{ mg/day}$ and the combination of OCS+AZA+NAC within 4 weeks of Visit 2, cyclophosphamide within 8 weeks of Visit 2, rituximab within 6 months of Visit 2. Equivalent Doses of Corticosteroids refer to [Appendix 10.3](#).

Note: Patients whose RA/CTD is managed by these medications should not be considered for participation in the current study unless change in RA/CTD medication is medically indicated (refer to [Inclusion Criterion #5](#))

8. Diagnosis of IPF based on ATS/ERS/JRS/ALAT 2018 Guideline [[R18-2794](#)].
9. Diagnosis of Systemic Sclerosis (SSc) based on 2013 ACR/EULAR classification
10. Significant Pulmonary Arterial Hypertension (PAH) defined by any of the following:
 - a. Previous clinical or echocardiographic evidence of significant right heart failure
 - b. History of right heart catheterization showing a cardiac index $\leq 2 \text{ l/min/m}^2$
 - c. PAH requiring parenteral therapy with epoprostenol/treprostinil

Proprietary confidential information © 2025 Boehringer Ingelheim International GmbH or one or more of its affiliated companies

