3.3.5.1 Discontinuation of trial treatment

Short term interruptions for adverse events (see also [Section 4.2](#)) are possible and should be used whenever possible to avoid permanent discontinuation of trial medication

The following will require a permanent discontinuation of trial treatment of an individual patient:

- The patient wants to discontinue trial treatment, without the need to justify the decision.
- The patient can no longer receive trial treatment for medical reasons (such as chronic use of concomitant medication, adverse events, other diseases that puts a patient at risk, parenteral feeding requirement or pregnancy).
- The patient experiences signs of hepatic injury, defined in [Section 5.2.6.1.4](#).
- No further dose reduction is possible for patients on the 100 mg bid regimen. In case of persistent adverse events observed at this dose, or severe effects at 150 mg bid, permanent treatment discontinuation should be considered.

Temporary interruption (see also [Section 4.2.1](#)) or permanent discontinuation of trial treatment is recommended (at the investigators discretion) for the following situations:

- Major surgery, including any abdominal or intestinal surgery.
- Major thrombo-embolic events e.g. stroke, deep vein thrombosis, pulmonary embolism, myocardial infarction.
- Increased risk of bleeding e.g. hemorrhagic CNS event, haemoptysis or haematuria, active gastro-intestinal bleeding or GI-ulcers.
- The patient experiences an infection with SARS-CoV-2.

The investigator, after assessment of available clinical data and taking into consideration the potential risks associated with administration of nintedanib, may decide not to permanently discontinue the trial medication. In such a case, continuation of treatment with trial medication should be discussed with the patient, and the decision and reasoning documented in the source data.

If a patient becomes pregnant during the trial, the investigational product must be stopped and the patient should be followed up until birth or otherwise termination of the pregnancy. The data of the patient will be collected and reported in the clinical trial report (CTR) until patient's last visit and any events thereafter will be reported in the BI drug safety database. Refer to [Section 5.2.6.2.3](#) for detailed information on event reporting in case of pregnancy.

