4.2.1.2 Management of liver enzyme elevation

Nintedanib can be associated with increased liver enzymes (see [Section 1.4.2](#)). Concomitant use of other drugs known to cause liver enzyme elevations should be evaluated. For a detailed guidance on how to manage liver enzyme elevations, please refer to [Table 4.2.1.2: 1](#).

Table 4.2.1.2: 1 Recommendations for managing liver enzyme elevations

	AST and/or ALT increase to			Signs of hepatic injury* (Section 5.2.6)
	>1.5x to <3x ULN	≥3x to <5x ULN and no signs of hepatic injury (see Section 5.2.6)	≥5x to <8x ULN and no signs of hepatic injury (see Section 5.2.6)	
Visit 2 (randomization)	Withdraw trial medication or justify continuation ¹	Withdraw trial medication	Withdraw trial medication	Withdraw trial medication
Any other Visit	Continue as planned ²	Reduce dose or interrupt trial medication ³	Interrupt trial medication	Withdraw trial medication
		Close observation ⁴ After 2 weeks or any time later	Close observation ⁴ After 2 weeks or any time later	CLINICAL EVALUATION OF HEPATIC INJURY (Section 5.2.6.1.4)
	<3x ULN	≥3x ULN	< 3x ULN	≥3x ULN
	Reduced: return to initial dose. Interrupted: restart at reduced dose. Monitor bi- weekly for at least 8 weeks	Permanently discontinue trial medication Close observation ⁴	Restart at reduced dose Monitor weekly for 4 weeks, then bi-weekly for at least 8 weeks	Permanently discontinue trial medication. Close observation ⁴

Footnotes:

* Signs of hepatic injury are defined as

- ALT and/or AST ≥8 fold ULN
- ALT and/or AST ≥3 fold ULN and total bilirubin ≥2 fold ULN
- ALT and/or AST ≥3 fold ULN and unexplained INR >1.5
- ALT and/or AST ≥3 fold ULN and unexplained eosinophilia (>5%)
- ALT and/or AST ≥3 fold ULN and appearance of fatigue, nausea, vomiting, right upper abdominal quadrant pain or tenderness, fever and/or rash

¹ Investigator to confirm in writing that continuation is justified (e.g. intermittent fluctuation of transaminases).

² According to visit schedule. Consider additional control visits as adequate.

³ To be decided by Investigator, based on individual risk assessment.

⁴ Close observation: Re-test ALT and AST, alkaline phosphatase, total bilirubin, and eosinophils within 48 to 72 hours, then approximately 7 days, then approximately 2 weeks by using intermediate visit laboratory kit.

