Category	Laboratory test
Biochemistry	Total protein, creatinine, electrolytes and liver function (AST, ALT, GGT, alkaline phosphatase, and total bilirubin)
Urinalysis	pH, glucose, erythrocytes, leukocytes, protein, nitrite (semi-quantitative measurements; -, +, ++, +++)
Local Urine dipstick pregnancy test in all women of childbearing potential. If urine test is not acceptable to local authorities, a blood test must be done at a local laboratory.	

At 'a-Visits', safety blood, pregnancy tests and urine samples will be collected and submitted to the central laboratory if needed for additional safety monitoring at the discretion of the investigator (see [Section 4.2.2.2](#) for additional safety monitoring).

The samples and pregnancy tests may be collected at the office of a local doctor using trial specific lab kits that will be sent to a central laboratory for analyses. These kits will be provided to patients at study visits as applicable.

Creatinine clearance will be calculated based on serum creatinine according to Cockcroft and Gault ([R96-0690](#), [Appendix 10.2](#)).

If laboratory values indicate abnormality, adequate and more frequent blood sampling may be performed at the discretion of the Investigator.

In case of liver function value elevations, close monitoring must be ensured by the Investigator. Refer to [Section 4.2.1.2](#) for monitoring elevations and [Section 3.3.5](#) for withdrawal criteria.

Laboratory analysis will be done using central laboratory services. Venous whole blood will be collected through the assigned central laboratory. Details regarding centrifuge, processing, storage and shipment of samples will be determined by the central laboratory in accordance with the Sponsor. The Investigators will be informed and instructed by the central laboratory and detailed documentation will be included in the ISF.

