6.2.2 Treatment period(s)

At the beginning of each visit during treatment phase, Investigator and site personnel should ensure the well-being of the patient as well as prepare all requirements for conduct of the visits that are necessary.

The order of the different trial procedures should follow the protocol and should be planned for taking into account the specific structure of the investigational site and following the mandatory needs outlined in the clinical trial protocol.

Mandatory needs: the following has to be ensured during trial visits according to the study Flow Chart.

- Patient reported L-PF Symptoms and Impact questionnaires have to be filled out always prior to any other procedures by the patient in a quiet area and in the following order.
- Urine pregnancy test and any laboratory sample collection must be performed prior trial medication administration.
- FVC measurement at all visits should be performed approximately at the same time of the day to reference time point at Visit 2.

Baseline Visit 2 (randomization)

The following prerequisites must be available for randomization:

- Eligibility confirmation and HRCT pattern from central HRCT review.
- Safety laboratory results including haemoglobin and creatinine from Visit 1.

Procedures:

- All patients will be asked to fill out the patient reported L-PF Symptoms and Impact questionnaires prior to any other visit procedure.
- Site personnel will review questionnaires for completeness.
- Physical examination including vital signs will be performed.

Proprietary confidential information © 2025 Boehringer Ingelheim International GmbH or one or more of its affiliated companies

- Adverse events and concomitant therapy since last visit will be reviewed and recorded.
- Medical history will be reviewed.
- Repeated resting 12-lead electrocardiogram using site's own equipment will be performed and evaluated if resting ECG was abnormal at Visit 1 (if possible prior to blood draw).
- FVC measurement will be conducted with the spirometer.
- All in/exclusion criteria will be assessed based on Visit 1 laboratory and Visit 2 measures.
- HRCT will be performed in patients who agree to have follow-up HRCT done as part of the trial, unless a screening HRCT was done as part of the study to determine eligibility.
- Safety blood and urine samples will be collected and submitted to the central laboratory.
- Local urine dipstick pregnancy test (if applicable).

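### For a Visit 2 AST/ALT of 3x to <8x ULN without hepatic injury, the liver table withdraws the drug, while Sections 3.3.3 and 6.1 allow a justified continuation with no ceiling

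*Protocol*

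**What the plan says.** Four parts of the protocol bear on a raised Visit 2 transaminase.

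- **Section 3.3.3, exclusion criterion 1 and the note after criterion 3.** AST and/or ALT above 1.5x ULN at Visit 1 excludes. If the Visit 2 results no longer meet the entry limits, "the Investigator has to decide whether it is justified that the patient remains on study drug", and the reasons are to be documented.
- **Section 6.1.** Visit 2 results come back only after the visit. If they would have met an exclusion criterion, "the patient should not continue receiving trial medication unless continuation is justified in writing by the Investigator".
- **Section 4.2.1.2, Table 4.2.1.2:1.** The Visit 2 cell for >1.5x to <3x ULN reads "Withdraw trial medication or justify continuation", with a footnote asking for written confirmation by the investigator. The cells for ≥3x to <5x and ≥5x to <8x ULN (both without hepatic injury), and for hepatic injury, give withdrawal alone. For all other visits the ≥3x to <5x cell reads "Reduce dose or interrupt trial medication", and the ≥5x to <8x cell calls for interruption.
- **Section 3.3.5.1.** The mandatory list opens with "The following will require a permanent discontinuation of trial treatment of an individual patient" and includes signs of hepatic injury, which by definition include ≥8x ULN, or ≥3x ULN with raised bilirubin, INR, eosinophils or symptoms.

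Section 5.2.3 adds that "In case of liver function value elevations, close monitoring must be ensured by the Investigator". It refers to Section 4.2.1.2 for monitoring and to Section 3.3.5 for withdrawal criteria.

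**The concern.** The general rule in Sections 3.3.3 and 6.1 applies to any Visit 2 breach of a laboratory entry limit. For AST/ALT it has no ceiling and does not mention the liver table. The table confines the justification route to values below 3x ULN. Between 3x and <8x ULN without hepatic injury, an investigator can therefore keep a patient on drug in line with 3.3.3 and 6.1 while departing from the table.

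The timing makes this a live question. Section 6.2.2 requires that "any laboratory sample collection must be performed prior trial medication administration", so the Visit 2 value is a pre-treatment value. The flow chart has the first dose given in clinic at that visit, and the result arrives later. The rule thus governs patients who have already started. The protocol says nintedanib can raise liver enzymes, and Section 1.4.2 lists Asian race among the risk factors for such elevations. A patient whose transaminases rose before any study drug could stay on 150 mg bid with no dose change attached.

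**Working it through.** The plan states no figure to reproduce; the check is mainly a comparison of rules.

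**Step 1. Rules by band for a Visit 2 AST/ALT result**

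| Visit 2 value | Table 4.2.1.2:1 | 3.3.3 note and 6.1 | 3.3.5.1 | Outcome |
|---|---|---|---|---|
| >1.5x to <3x ULN | Withdraw or justify | Stop unless justified | Not triggered | Consistent |
| ≥3x to <5x ULN, no hepatic injury | Withdraw | Stop unless justified | Not triggered | Conflict |
| ≥5x to <8x ULN, no hepatic injury | Withdraw | Stop unless justified | Not triggered | Conflict |
| Signs of hepatic injury, including ≥8x ULN | Withdraw | Stop unless justified | Permanent discontinuation required | Settled by 3.3.5.1 |

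At 2x ULN the rules agree. At 4x or 6x ULN the table gives withdrawal with no alternative, while 3.3.3 and 6.1 leave continuation open. Withdrawing complies with every section, so the defect is the uncapped exception, not an impossible instruction.

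**Step 2. Does any section rank the rules?** Sections 3.3.3 and 6.1 do not mention the table. The table is titled as recommendations and does not mention 6.1. The withdrawal reference in 5.2.3 leads to 3.3.5, whose liver criterion is hepatic injury and so misses this band.

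**Step 3. Comparison with later visits.** From Visit 3 on, ≥3x to <5x ULN calls for reduction or interruption, and ≥5x to <8x for interruption. Section 6.1 attaches neither to a justified continuation at Visit 2. Its exception is therefore looser than the table's rule for patients already established on drug.

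**Step 4. Size of the rise.** The qualifying value was at most 1.5x ULN.

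- Smallest rise: 3 / 1.5 = 2.0-fold.
- Upper end of the band relative to the entry ceiling: 8 / 1.5 = 5.3, so values lie below about 5.3 times that ceiling.

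**Step 5. Exposure before the next scheduled safety laboratory.** The flow chart puts this at Visit 3, day 15 ± 3. Section 4.1.4 gives 2 capsules per day. Counting from Day 1, capsules = (day − 1) × 2:

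- Day 15: 14 × 2 = 28
- Day 12: 11 × 2 = 22
- Day 18: 17 × 2 = 34

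These totals include capsules taken before the Visit 2 result returns, which no rule can prevent. Laboratory turnaround is not given, so the avoidable part is some unknown amount less. The totals also assume no earlier unscheduled test.

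**The case against.** The best counter-argument is that the specific rule displaces the general one. The 3.3.3 note and 6.1 cover all laboratory entry limits. The liver table has its own Visit 2 row graded by ULN, and Section 4.2.1.2 directs readers there for detailed guidance. Its footnote repeats the written-justification mechanism and attaches it to the lowest band only, which may be where the authors meant the exception to apply. The default under 6.1 is also to stop, so continuing would take a written justification against an explicit withdrawal cell.

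That reading is sensible, and probably what was intended. It is not stated, however, and the table's title as recommendations makes it just as easy to treat 6.1 as the operative rule.

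Other safeguards narrow the gap. Close monitoring is required, a repeat value ≥3x ULN would fall under the table's row for other visits, and hepatic injury forces discontinuation. The unprotected case is an isolated, asymptomatic value of 3x to <8x ULN, justified in writing and not promptly retested. Under 2:1 allocation, about two thirds of such patients would be on nintedanib. These points limit the number affected and the added exposure; they do not make the rules agree.

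**Conclusion.** The concern holds. For a Visit 2 AST/ALT of ≥3x to <8x ULN without signs of hepatic injury, the protocol gives two different answers and no order of precedence. The conflict is confined to that band.

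It concerns patients whose transaminases at least doubled from a qualifying value before treatment. If continued at full dose, they would have taken about 28 capsules (22 to 34) by the next scheduled laboratory, part of them before the result was known. The documents give no frequency, and few patients are expected. The conclusion rests on reading each section as written, without assuming that the table silently limits 6.1. It is a patient-safety and deviation-classification issue that should be corrected, with no bearing on the sample size or the primary model.

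**What to change.** Add to the 3.3.3 note and to 6.1:

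> For AST/ALT, continuation may be justified only for values >1.5x to <3x ULN. At ≥3x ULN, Table 4.2.1.2:1 governs and trial medication is withdrawn.

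Keep the present justify-and-document rule for the other laboratory criteria.

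The cost is a wording change by amendment or administrative letter, a route the sponsor has already used for clarifications in this trial, and slightly less investigator discretion in a few patients. Withdrawn patients are asked to keep attending visits, and any FVC they provide still enters the primary analysis under Protocol 7.2.2 and SAP 7.4.1. Those data are retained only if the patients attend.

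The documents do not state recruitment status. If randomization has closed, the equivalent step is to identify any Visit 2 AST/ALT values ≥3x ULN and to settle, before unblinding, which rule defines a deviation under SAP 6.2.
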